**VERSION DATE: May 31, 2022** 

### **RELATED STUDIES:**

- STU00206086: Communication Bridge: A person-centered Internet-based intervention for individuals with primary progressive aphasia.
  - 1) This study will extend the STU00206086 protocol for up to 30 participants and their communication partners who completed, were screened for, were placed on the waitlist for, or new persons meeting the eligibility criteria for the study. The objective is to evaluate the effectiveness of evidence-based interventions on individuals living with PPA and their ability to communicate after treatment, but for a longer duration of time (3 session blocks over ~18-months, see figure and detailed description below) in order to examine further stages of the disease.

Check any **applicable** boxes in the table below – you will be asked for further detail on these topics later in the protocol form:

Indicate Vulnerable Population(s) to be Enrolled	☐ Children (you must complete Appendix A in addition to this protocol document if you plan to enroll children)  ☑ Cognitively Impaired Adults ☐ Pregnant Women (IF the research activities will affect the pregnancy or the fetus) ☐ Prisoners (or other detained/paroled individuals)
International Research	
(check this box if you will	
collect data from	
individuals located outside	X
the United States)	
Research involving external	
collaborators (some	
research activities will be	
carried out by individuals	
not employed by	X
Northwestern or NU affiliates)	
Research has U.S. Federal	
government funding via	
direct award or a sub-award	
(e.g., NIH, NSF, other	
federal agencies or	
departments)	

## 1.0 Purpose and rationale of the study:

The purpose of this study is to evaluate the effectiveness and feasibility of evidence-based interventions in individuals living with primary progressive aphasia (PPA) that address communication-focused outcomes. By extending the intervention to include social work our aim is to address psychosocial and communication concerns that may have emerged as a result of their progressive neurodegenerative condition, and/or potentially slow the inevitable decline of functional communication that occurs as a consequence of PPA. The study will enroll individuals who have completed, were screened for, were placed on the waitlist for, or new persons meeting the eligibility criteria for the related study, STU00206086, to understand the added benefit of adding social work to the intervention. The intervention will be provided remotely by speech-language pathologists and social workers using a HIPAA compliant Zoom license, provided by Northwestern University. This study will be a continuation of one of the largest non-pharmacologic intervention studies for individuals with PPA to date. It will add critical information regarding the effectiveness of telepractice interventions for communication disorders in adults with primary progressive aphasia specifically, and in

dementia more broadly. The information gained will be especially important for understanding the psychosocial needs of individuals and in different stages of the disease, a topic that is currently not covered in research.

**Aim:** Understand the added benefit and feasibility of multicomponent (speech-language therapy and social work) intervention for individuals who have completed, were screened for, were placed on the waitlist for, or new persons meeting the eligibility criteria for the related study, STU00206086

### **Background:**

Primary Progressive Aphasia. The diagnosis of primary progressive aphasia (PPA) is made when a relatively isolated and progressive impairment of language that occurs as a result of a neurodegenerative disease process. It is associated with Alzheimer's disease and/or a form of frontotemporal lobar degeneration. Adults with PPA can have deficits in word finding, word usage, word comprehension, and/or grammar, among other language impairments. Consensus research criteria recognize three variants of PPA based on the profile of language deficits: agrammatic (PPA-G), semantic (PPA-S) and logopenic (PPA-L).

Speech and language intervention for language impairments associated with PPA. Promising case-reports and small group studies of non-pharmacological communication interventions in PPA show positive effects of impairment-based and participation-based interventions (i.e., script training to improve fluency, multi-syllabic word production training to improve articulation; for reviews see). However, with few exceptions (our current RCT) there are no gold-standard randomized control trials, which limits the ability to move this research into mainstream clinical implementation. Importantly, few studies have extended intervention and data collection beyond a 6-to-12-month window or included social work, and none have done so at the group level. As such the longer-term benefits of extended multi-component interventions on maintaining communication abilities, preserving participation in functional communication activities, and slowing language impairment progression remain unexamined. We will address this concern by enrolling a subset of consenting participants into a multi-component intervention to examine whether we are able to address both functional and psychosocial needs of the individuals living with PPA.

Telepractice model. Access to services and the ability to conduct large evidence-based studies has been limited because individuals with PPA may not live near an SLP who has experience in treating individuals with neurodegenerative aphasia. In fact, >40% of the participants in our preliminary Communication Bridge study lived in rural areas and >94% lived outside Chicago, IL, the home site for the study. Distance from a healthcare facility is one of many variables that can be alleviated using a telepractice model. The intervention in this protocol will be deployed via a telehealth service delivery approach. This is consistent with our in-progress Phase-2, 12-month, study and also our pilot study. To date, 33 people have completed our 12-month study using our Communication Bridge web-based portal and a video-conferencing platform without any significant issues or concerns.

Social work component. In this protocol, we augment the intervention provided in our base 12-month protocol by adding a social work component alongside the speech-language pathology intervention. The combined, multi-disciplinary intervention approach is designed to address the psychosocial impairments that may interact with language impairments to negatively impact communication outcomes in individuals with PPA. Individuals with PPA tend to have preserved insight into their disease, which may contribute to increased risk for depression. Onset of PPA tends to be before the age of 65, which is younger than those with amnestic Alzheimer's dementia. This creates unique psychosocial and economic challenges since adults with PPA are commonly in the prime-earning phase of their careers and often have dependent children at home. Social workers can help families navigate the difficult decisions related to their diagnosis. Here we will provide a multi-component intervention to examine whether we are able to address both functional and psychosocial needs of the individuals living with PPA.

# 2.0 Enrollment Criteria (who can be in your study and who would not be eligible to participate in your study):

Must have completed, were screened for, were placed on the waitlist for, or new persons meeting the eligibility criteria for the related study STU00206086 within the last 24 months and maintain eligibility criteria:

- Must speak English as their primary language and have sufficient proficiency in English for completing all assessment and treatment activities
- Hearing adequate to have a conversation in a crowded room(correction permitted)
- Reported vision adequate to read the newspaper (correction permitted)
- Must have a communication partner (spouse, family member, close friend) who is willing to participate in the study
- Adequate experience with computers
- Diagnosis of PPA must be made by a clinician
- Must be 18 years or older
- Must have the ability to consent

## 3.0 Sample Size:

Up to 30 individuals with PPA and their communication partners (spouse, family member, or close friend) will be enrolled. A formal sample size estimate and power analysis was not completed as this is a feasibility study to examine the added benefit of extended multi-component treatment for persons with PPA. Data from this Phase I expansion of our current Phase II trial will be used to establish feasibility of the protocol, to make protocol adjustments, and to collect preliminary effectiveness data for an upcoming grant submission.

## 4.0 Recruitment and Screening Methods:

This study will only recruit participants from four routes:

- Participants completed the related study (STU00206086). When they consented to that study, they selected "I agree" to be contacted for future studies.
- Participants were screened for the related study (STU00206086) and were not eligible to participate and voluntarily signed up for the Mesulam Center Research Registry (which could have occurred before or after they were screened). The Mesulam Center Recruitment Registry is housed within the Alzheimer's Disease Core Center IRB-approved protocol (STU00023196). Participants residing in the European Economic Area will not be contacted for this study. There will be no external recruitment strategies needed. Potential participants will be contacted by the study team, with whom they already have an established relationship. Participants will be emailed the initial recruitment script (see supporting document) and asked if they would like to enroll in this study.
- Participants were placed on the waitlist for the related study (STU00206086) due to the high volume of interest and limited enrollment capacity. All participants were added to the waitlist after voluntarily signing up for the Mesulam Center Research Registry. Individuals who were seen at NMH's Neurobehavior and Memory Clinic will have a HIPAA authorization in their consent form to grant approved study team members access to their medical records through an Enterprise Data Warehouse (EDW) exception. Individuals who were not seen at NMH will be asked to send in their own medical records and will not require a HIPAA authorization. We will verify these individuals as meeting eligibility criteria through medical records and a brief screening by our team.
- New persons meeting eligibility criteria for the related study (STU00206086) who contacted the study team after enrollment closed. Individuals who were seen at NMH's Neurobehavior and Memory Clinic will have a HIPAA authorization in their consent form to grant approved study team members access to their medical records through an Enterprise Data Warehouse (EDW) exception. Individuals who were not seen at NMH will be asked to send in their own medical records and will not require a HIPAA authorization. We will verify these individuals as meeting eligibility criteria through medical records and a brief screening by our team

If the participant is interested, a screening call will occur over phone or video-chat. During this interest call, a study team member will complete a brief screening discussion (see supporting document) to assess whether the participant has experienced any significant life or medical changes since being screened for or completing STU00206086 that affect eligibility. A summary of this conversation will be stored in the REDCap project.

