# 7.0 International Research (where data collection will occur outside the United States and U.S. territories, including online activities)

International participants, excluding those from the European Economic Area, may be enrolled if they meet all eligibility criteria, including using English as their primary language. Similar to domestic participants, international participants will join all study visits using the iPad provided for them. All data collection will take place from Northwestern University and our approved collaborator at OHSU. An external IRB review will not be obtained since Northwestern will remain the primary study site. In accordance with Northwestern's policy, the Institution's human research activities, regardless of whether the research is subject to the U.S. Federal Policy for the Protection of Human Subjects, will be guided by an assurance of specific principles governing the institution in carrying out its responsibilities for protecting the rights and welfare of humans in research conducted at or sponsored by the institution.

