## 9.0 Research with Vulnerable Populations

Vulnerable Populations: Individuals with Primary Progressive Aphasia are cognitively impaired. However, individuals in the mild stages of Primary Progressive Aphasia have deficits primarily in the use of language. Memory, attention, and other cognitive abilities are preserved. When the individuals enrolled or were screened in the related study, they were verified as being in the mild stages of the disease through medical records and a brief evaluation by our team. Although some disease progression is expected, we anticipate (based on more than 15 years of working with this population) participants will be able to understand and complete the consent process. We will gather medical records and conduct a screening for the individuals placed on the waitlist and new persons who contacted the study team after enrollment closed for the related study to determine eligibility. To aid with comprehension, participants with PPA will be consented with their communication partner. Their communication partner will also be consented into the study. This study provides an intervention for a population that has no pharmacological treatment for their disease, and thus a benefit for them to more effectively cope with their symptoms.

Individuals will be provided with the opportunity to speak with members of the study team, including speech-language pathologists, prior to consent and enrollment to ask any

questions they have. The study team members, including SLPs and social workers, are trained in communicating with individuals of this population.

To confirm that participants have the ability to provide their own consent, individuals with PPA will complete a consent assessment task with the research coordinator after reviewing the consent from. The task will prompt the participant to respond, either verbally or by pointing, to yes or no questions regarding information discussed in the consent form. If nonverbal answers are provided, the communication partner will aid in relaying the participant's gestural answers. During this task, the research coordinator may need to provide clarification on any areas of confusion. This assessment task will provide documentation of the participant's understanding and consent (see supporting documents). The assessment task template is based on a task used in the ACT NOW international clinical trial (NCT00831740).

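### Does asking entrants to maintain eligibility conflict with recruiting people who failed screening for the related study?

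*Protocol*

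**What the plan says.** Section 2.0 opens its entry criteria with "Must have completed, were screened for, were placed on the waitlist for, or new persons meeting the eligibility criteria for the related study STU00206086", adds "within the last 24 months and maintain eligibility criteria", and after a colon lists eight items: English, hearing, vision, a willing communication partner, computer experience, a clinician's diagnosis of PPA, adult age and ability to consent.

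Section 4.0 states "This study will only recruit participants from four routes". The routes are people who completed the related study, people who were screened for it and failed, people on its waitlist, and new persons who made contact after it closed. The second is worded "Participants were screened for the related study (STU00206086) and were not eligible to participate". For the waitlist and new-person routes the section adds that eligibility will be verified from medical records and a brief screening. For anyone interested, a call establishes "whether the participant has experienced any significant life or medical changes since being screened for or completing STU00206086 that affect eligibility", and a summary goes into REDCap.

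Section 7.0 says that international participants "may be enrolled if they meet all eligibility criteria, including using English as their primary language". Section 9.0 says of those who enrolled in or were screened for the related study that "they were verified as being in the mild stages of the disease through medical records and a brief evaluation by our team".

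**The concern.** To maintain a status one must already have it. A person who failed screening for the related study did not have that study's eligibility, so the criterion in Section 2.0 and the second route in Section 4.0 appear incompatible. If the verb could be read in several ways, two screeners might decide differently on the same candidate, and an enrolment valid on one reading would be an eligibility deviation on another. That would affect who makes up the sample of up to 30 dyads from which Section 3.0 expects feasibility and preliminary effectiveness data.

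Two further features add to the unease. The call is framed as a question about changes, which suits someone who was eligible before better than someone who was not. And the Section 9.0 statement that people were verified as mild makes no exception for those who failed screening.

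**Working it through.** The protocol gives no figure on this point, so the check sets the possible readings against the kinds of candidate and then asks which readings the text supports.

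**Inputs.** Eight listed items, none of them disease stage (Section 2.0). Four routes, one of them for screen failures (Section 4.0). The related study's own criteria are not shown, nor is the number of candidates on any route.

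**Step 1: all readings taken at face value.** The kinds of candidate are:
- A: failed a listed item then and still fails it.
- B: failed a listed item then and meets all eight now.
- C: meets all eight, but failed and still fails a criterion of the related study that is not listed here.

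| Reading of the verb | A | B | C | Kinds admitted |
|---|---|---|---|---|
| Was eligible for the related study and still is | out | out | out | 0 of 3 |
| Met the eight items then and meets them now | out | out | in | 1 of 3 |
| Meets all the related study's criteria now | out | in | out | 1 of 3 |
| Meets the eight items now | out | in | in | 2 of 3 |

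The decision agrees for A and differs for B and C, that is, for 2 of 3 kinds. This counts logical categories, not people. Kind C also exists only if the related study had criteria beyond these eight. If it did not, C is empty and 1 of 2 kinds differs.

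**Step 2: which readings survive the text.**
- *Was and still is eligible for the related study.* This admits nobody from the second route. The protocol names the screened group under Related Studies and in Sections 1.0 and 2.0, and describes it in Section 4.0. A reading that cancels a route written on purpose is not one that a screener would adopt.
- *Meets all the related study's criteria now.* In Section 2.0 the reference to that study's criteria is attached to new persons. The criteria to be maintained come after the colon, and they are the eight items.
- *Met the eight then and now.* Section 2.0 does not mention the result of the earlier screening. The verb also governs all four groups, and new persons have no earlier result to maintain. For them, and for the waitlist, Section 4.0 describes verification that they meet the criteria. The verb therefore cannot carry a then-and-now sense throughout.
- *Meets the eight now.* This fits all four routes, the mostly present-tense wording of the items, and the standard in Section 7.0.

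Once one reading is applied throughout, 0 of 3 kinds differ.

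**Step 3: whether the call can apply that reading.** The question covers changes that affect eligibility and is not limited to changes for the worse. A candidate who lacked a partner and now has one (kind B) reports just such a change. A candidate who failed a listed item and reports no change is kind A, out on every reading.

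**Step 4: other checks at entry.** Sections 9.0 and 11.0 test ability to consent with a task. Section 8.0 has the partner consented at orientation, where health information is also updated. At least two of the eight items are thus established at entry whatever the verb means. Section 6.0 gives all enrolment decisions to the team at one institution.

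**Step 5: the mild-stage sentence.** A person can fail screening for a reason other than stage and still have been verified as mild. The text does not show the sentence to be false, and stage is not an entry criterion here.

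**The case for a change.** The best case for a change is that the clash is on the page, in two current passages, on a matter that a statistical analysis plan would not settle. Section 4.0 promises verification for the waitlist and new-person routes but has no matching sentence for screen failures. Nothing says that the reason for the earlier failure is compared with the Section 2.0 list. The Section 9.0 sentence supports the expectation that participants can complete consent, so it should be true of everyone it covers. Amending a few words would cost little.

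Part of this stands. The verb is imprecise for the second route, the mild-stage sentence is broader than it needs to be, and the text does not describe how an earlier failure is handled. The call script that might cover this is a supporting document that is not shown.

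The consequence does not stand. Differing decisions require readings that the rest of the protocol rules out or, for kind C, criteria that nobody can see here. Consent is protected by the assessment task rather than by the mild-stage sentence. To declare the eight items the sole standard for this route would also settle an eligibility question that belongs to the sponsor, without sight of the related study's criteria.

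**Conclusion.** No change to the plan is called for. This is loose drafting that the enrolling team can be expected to fill sensibly: candidates from the second route must meet the eight Section 2.0 items at entry. The scope is one of four routes; the number of people concerned is unknown, so no share of the 30 places can be stated. No wrongful entry is shown. Section 3.0 reports no power analysis, so no sample-size figure or error rate could shift, and the study's purpose of gathering feasibility and preliminary data is not affected.

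The conclusion rests on two assumptions: that the colon in Section 2.0 ties the verb to the listed items, and that the call is used to check those items in either direction. Both follow the ordinary sense of the text. Tidier wording would make the document read better but would alter no entry decision under that reading.

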#### **5.0** Research Locations:

The research team will be located at the Mesulam Center for Cognitive Neurology and Alzheimer's Disease. Speech language pathologists and social workers that provide treatment for the study will come from Northwestern University and Oregon Health and Science University.

All research and data collection visits will take place online over a HIPAA-compliant Zoom software. This study does not require any in-person visits. The potential participants who will enroll in this study come from all over the United States or international countries, excluding the European Economic Area, and will connect to the study visits from their home.

# 6.0 Multi-site Research (research that involves external collaborating institutions and individuals):

The individuals from OHSU are clinicians on the current study. However, all hard copies of data and coordination for the study will take place at NU. Enrollment decisions will be made by the team at NU and participants will be assigned to one of the clinicians. All recruitment, enrollment, and consenting procedures take place at NU. We are using these clinicians because they are experts in treating individuals with primary progressive aphasia, which is rare.

The researchers joining us from OHSU are [name], M.S., CCC-SLP, speech-pathologist and [name]. Both researchers are listed as Co-Investigators. [name] will be seeing participants as a treating clinician. [name] will not see participants for the study but will play an advisory role and have access to participant data. An IAA has been established between Northwestern University and OHSU. Northwestern University will serve as the IRB of Record.

